An Analysis of Covariance (ANCOVA) will be used to analyse the primary endpoint: change in Hb concentration from baseline to Week 16. Missing change from baseline hemoglobin concentration data for week 16 will be imputed using multiple imputation methodology. This will generate 10 complete datasets containing imputed values for those missing in the original dataset. Hb concentrations at baseline, Week 4, Week 8 and gender will be considered as variables helpful in guiding this imputation. For each imputed dataset, the change from baseline to Week 16 complete datasets will be analysed using analysis of covariance (ANCOVA) with factors for treatment and disease and a covariate of baseline hemoglobin and eGFR. By combining the results from these analyses, the treatment estimates will be constructed using the parameter estimates and associated standard errors. Similarly the difference of the adjusted treatment means (ferric maltol – placebo) will be presented with the associated standard error and 2-sided 95 % confidence interval. The primary endpoint analysis will be performed using the intention-to-treat (ITT) population.

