6.3.1 Inclusion Criteria

All of the following criteria must be met to randomize a subject in the study:

1. Ability to understand the information given in the Independent Ethics Committee (IEC) or Institutional Review Board (IRB) approved information sheet and consent form. Must sign and date the informed consent and authorization to use protected health information (PHI) in accordance with national and local subject privacy regulations prior to any study mandated procedure.
2. Willing and able to comply with study requirements.
3. Age \geq 18 years at the time of informed consent.
4. A current diagnosis of CKD with an estimated glomerular filtration rate (eGFR) of <60 mL/min/1.73m² and ≥ 15 mL/min/1.73m², as calculated using the abbreviated version of the Modified Diet in Renal Disease equation (MDRD) assessed via screening laboratory results.
5. Iron deficiency anemia defined by the following criteria assessed via screening laboratory results:
 - a. Hb <11.0 g/dL and ≥ 8.0 g/dL
 - b. AND ferritin <250 ng/mL with a Transferrin saturation (TSAT) $<25\%$ OR ferritin <500 ng/mL with a TSAT of $<15\%$
6. Female subjects of childbearing potential (including perimenopausal females who have had a menstrual period within 1 year prior to screening) must agree to use a reliable method of contraception until study completion and for at least 4 weeks following their final study visit. Reliable contraception is defined as a method which results in a low failure rate, i.e., less than

1% per year when used consistently and correctly, such as implants, injectables, some intrauterine contraceptive devices (IUDs), complete sexual abstinence, a vasectomized partner and oral contraceptive medications. Female subjects who are surgically sterile (bilateral tubal ligation, bilateral oophorectomy or hysterectomy) or postmenopausal (defined as no menstrual period within 1 year of screening) are also allowed to participate.

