8.2 RANDOMIZATION

A final eligibility evaluation must be conducted immediately prior to randomization. If a subject is deemed eligible a centralized IXRS/randomization system will be used to assign the subject to ferric maltol or placebo.

Subjects will be randomized in a 2:1 ratio (ferric maltol:placebo) and will be stratified according to the subjects baseline Hb (<9.5 or ≥ 9.5 g/dL) and eGFR (≤ 30 or >30 mL/min/1.73m²).

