8.3 BLINDING PROCEDURES

The Investigator and site staff, subjects, monitors, Sponsor and CRO staff will remain blinded to the treatment assignment during the conduct of the randomized phase of the study. The randomization codes will be released to the Sponsor for the purpose of the primary analysis only when the clinical database for the randomized phase of the study has been locked and a final Statistical Analysis Plan (SAP) is in place.

[figure not shown]
The randomization list is kept strictly confidential. It is accessible only to authorized persons who are not involved in the conduct and analysis of the study until time of un-blinding. The IXRS system will allow un-blinding by the vendor used by the Sponsor for reporting of suspected unexpected serious adverse reactions (SUSAR) as required by the regulatory agencies. The evaluation and decision as to whether a Serious Adverse Event (SAE) qualifies as an SUSAR is the responsibility of the Sponsor.

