9.3 DEMOGRAPHICS AND MEDICAL HISTORY

The following will be documented at screening and updated (if required) prior to randomization: year of birth, race and ethnicity, gender, all current medical conditions, all medical history relevant to IDA and or CKD regardless of onset and all known iron replacement therapies. Additionally, clinically significant medical history from the past 5 years will be documented including malignancies, sterilisations, hospitalizations, surgeries, ESA treatment history and the method of contraception for female subjects of childbearing potential.

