11.2 STATISTICAL METHODS

11.2.1 Primary Endpoint Analysis

Effectiveness will be analysed by determining whether the Test group shows a statistically significant superiority as compared to the Control group.

An Analysis of Covariance (ANCOVA) will be used to analyse the primary endpoint: change in Hb concentration from baseline to Week 16. Missing change from baseline hemoglobin concentration data for week 16 will be imputed using multiple imputation methodology. This will generate 10 complete datasets containing imputed values for those missing in the original dataset. Hb concentrations at baseline, Week 4, Week 8 and gender will be considered as variables helpful in guiding this imputation. For each imputed dataset, the change from baseline to Week 16 complete datasets will be analysed using ANCOVA with factors for treatment and disease and a covariate of baseline hemoglobin and eGFR. By combining the results from these analyses, the treatment estimates will be constructed using the parameter estimates and associated standard errors. Similarly the difference of the adjusted treatment means (ferric maltol – placebo) will be presented with the associated standard error and 2-sided 95 % confidence interval.

The primary endpoint analysis will be performed using the intention-to-treat (ITT) population.

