11.2.2 Secondary and Exploratory Analyses

Details regarding methods for analysis of secondary endpoints will be provided in the Statistical Analysis Plan (SAP). The SAP will also detail the analysis of exploratory and long-term endpoints.

No formal multiple comparisons procedure will be used to control the type I error rate for the analysis of secondary or other exploratory endpoints, including those defined for the long-term open-label phase of the study. For these analyses, confidence intervals and/or p-values will be displayed for descriptive purposes only.

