11.2.3 Sensitivity Analyses

For the primary endpoint, the following sensitivity analyses will be performed:

- The primary analysis defined in Section 12.2.1 (with multiple imputation) will be repeated using the per protocol (PP) population.
- The ANCOVA will be repeated for the ITT population but based on observed data only (complete case analysis without imputation).

- The ANCOVA will be repeated for the ITT population but using last observation carried forward (LOCF without imputation)
- A mixed model for repeated measures (MMRM) ANCOVA will be conducted using observed data only.

Other sensitivity analyses will be documented in the SAP.

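### Does the undefined 'disease' factor in the primary ANCOVA make the confirmatory model wrong?

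*Combined protocol and SAP*

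**What the plan says.** The model sentence appears twice. Section 11.2.1 has the Week 16 change analysed "using ANCOVA with factors for treatment and disease and a covariate of baseline hemoglobin and eGFR", and the Statistical Methods part of the synopsis repeats it: "with factors for treatment and disease and a covariate of baseline hemoglobin and eGFR". Neither place explains 'disease'.

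The other sections that bear on it are these:

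- Section 6.3.1 requires every subject to have a current CKD diagnosis within a stated eGFR range, and iron deficiency anemia by Hb, ferritin and TSAT limits.
- Section 8.2 says subjects "will be stratified according to the subjects baseline Hb" (cut at 9.5 g/dL) and eGFR (cut at 30). There is no disease stratum.
- Section 9.3 collects "all medical history relevant to IDA and or CKD regardless of onset", but builds no disease category from it.
- Section 8.3 holds the codes back until the randomized-phase database "has been locked and a final Statistical Analysis Plan (SAP) is in place".
- Section 11.2.2 leaves secondary, exploratory and long-term methods to the SAP. It does not mention the primary model.
- Section 11.2.3 reuses the model, for example: "The ANCOVA will be repeated for the ITT population but based on observed data only". The per-protocol and LOCF analyses reuse it as well.

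**The concern.** This is the trial's one confirmatory model, and one of its four named terms has no meaning in the text. The identical wording in both places means that neither can be used to interpret the other. The term is not a stratification factor under another name, because both strata already enter as covariates.

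If 'disease' means CKD or iron deficiency anemia, the factor is constant and its coefficient cannot be estimated. If it means something else, such as CKD stage or cause of CKD, somebody has to choose the variable and its levels. Two statisticians working from section 11.2.1 could then fit different models and report different primary estimates and p-values. If the choice were made after seeing results by arm, type I error would rise. The same term passes into the three sensitivity analyses that repeat the ANCOVA.

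**Working it through.** **Inputs.** From section 11.1: difference 1.0 g/dL, common SD 1.5 g/dL, 90 ferric maltol and 45 placebo, two-sided 0.05, stated power 95%, drop-out 20%, about 168 recruited. From section 11.2.1: treatment, baseline Hb, eGFR and 'disease'.

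**1. The plan's own figures.**

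- SE of the difference = 1.5 × √(1/90 + 1/45) = 0.274 g/dL.
- Noncentrality = 1.0 / 0.274 = 3.65.
- Power = 95.5% by the normal approximation and 95.2% by the noncentral t with 133 df.
- Placebo group needed for 95% power = (1.960 + 1.645)² × 1.5² × (1 + 1/2) / 1.0² = 43.9, so 44, or 132 in total at 2:1, against the stated 135.
- Recruitment = 135 / 0.80 = 168.75, against about 168.

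The stated figures reproduce. The calculation is a plain two-group comparison that makes no use of 'disease'.

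**2. Literal reading: one level.** Every subject has CKD and iron deficiency anemia, so the factor adds a column equal to the intercept. In a simulated trial of 90:45 with baseline Hb uniform on 8 to 11 and eGFR uniform on 15 to 60:

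| | Without the term | With the constant term |
|---|---|---|
| Rank of design matrix | 4 (of 4 columns) | 4 (of 5 columns) |
| Treatment estimate (g/dL) | 0.7497 | 0.7497 |
| SE (g/dL) | 0.2557 | 0.2557 |
| Residual df | 131 | 131 |

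Some software drops the column and some stops with an error. Neither produces a different treatment result.

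**3. Readings that need an invented variable.** The protocol gives none, so everything in this step is assumed: three-level CKD stage (eGFR cut at 30 and 45), or a four-level cause of CKD explaining 0%, 5% or 10% of outcome variance. The table shows the absolute shift in the treatment estimate against the model without the term, from 20,000 simulated trials per setting.

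| Assumed factor | Median (g/dL) | 95th percentile (g/dL) |
|---|---|---|
| CKD stage | 0.02 | 0.07 |
| Cause, 0% | 0.023 | 0.088 |
| Cause, 5% | 0.045 | 0.150 |
| Cause, 10% | 0.060 | 0.190 |

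- Type I error of each single model: 4.8% to 5.1%.
- Power, counting only lost degrees of freedom: 95.20% with 131 df and 95.19% with 128 df (four levels).
- At a true difference of 1.0 g/dL, adding the term changed whether p < 0.05 in about 1.0% of trials for stage and 1.3% to 3.0% for cause (8,000 trials per setting). With no true difference the range was 0.9% to 3.1%.

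**4. Picking the best model after unblinding.** Taking the smallest p-value from three models (no factor, an assumed two-level factor, an assumed four-level factor) gave a type I error of about 6.2% over 4,000 null trials. It was about 7.4% when the two-level factor had an assumed 1.0 g/dL effect on outcome. This requires the choice to be made with the codes in hand, and section 8.3 requires a locked database and a final SAP first.

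**The case for a change.** The strongest case for a change is that a confirmatory model should be fittable from the protocol alone, and this one strictly is not. Section 11.2.2 hands secondary, exploratory and long-term methods to the SAP and says nothing of the kind about the primary model. A SAP that quietly dropped or defined 'disease' would therefore depart from the protocol's wording. At the 95th percentile the assumed factors move the estimate by up to 0.190 / 0.274 = 0.7 SE, enough to tip a borderline p-value. Striking the term would also be cheap.

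Part of this stands. The term is undefined in the text, it looks superfluous, and the wording is untidy in a place where precision matters.

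The rest carries less weight. The 0.7 SE figure is a 95th percentile under the most prognostic of the assumed factors; the medians are 0.02 to 0.06 g/dL. CKD stage is a function of eGFR, which is already a covariate. Silence in section 11.2.2 does not prevent a SAP from clarifying the primary model, and section 8.3 makes a final SAP a condition of the primary analysis. Settling the term at that point is ordinary SAP work done blind to treatment, and any single reading fixed then is a valid test.

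**Conclusion.** The concern does not call for a change. The documents support only the one-level reading, and under it the plan as written gives the same estimate, SE, degrees of freedom, p-value and 95.2% power as the plan with the term removed. Deleting it would alter no result. A multi-level reading needs a variable from outside the protocol. Even then type I error stays at about 5% and the significance conclusion differs in roughly 1% to 3% of simulated trials.

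This rests on two things. The first is that 'disease' is either constant or settled in the final SAP before the codes are released, as section 8.3 requires; a choice made afterwards could take type I error to about 6% to 7% under the assumptions shown. The second is that the levels, variance shares and covariate distributions in the simulations are assumed, because the protocol gives none. The supplied text contains no separate SAP, so whether the term was later defined cannot be seen. The finding is limited to a term left undefined in the protocol, a gap that analysts fill sensibly and without consequence for the test.

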4 BACKGROUND INFORMATION

4.1 OVERVIEW OF DISEASE

IDA is commonly associated with chronic kidney disease (CKD) and it is one of the leading causes of morbidity and mortality (Regidor 2006; Hsu 2002). It is appropriate to administer regular iron replacement therapy as part of standard medical care (Post 2006; KDOQI 2006). IDA can be due to multiple factors, most significantly lack of production of erythropoietin, blood loss through gastrointestinal (GI) bleeding, medical procedures and/or impaired dietary iron absorption (Lopez 2015). In some patients there may be an inflammatory component to their CKD, and chronic inflammation can make absorption and utilization of iron less efficient compared to the normal state (Zaritsky 2009). Anemia can be found in CKD patients receiving dialysis and also in non-dialysis dependent CKD (ND-CKD) patients (Gotloib 2006; Post 2006). IDA is defined by lower than normal hemoglobin (Hb), ferritin and transferrin-saturation (TSAT) levels (KDOQI 2006).

The incidence of anemia varies with the severity or stage of CKD; the percentage of patients with haemoglobin ≤ 12 g/dL increases from 26.7% to 75.5% when glomerular filtration rate decreases from ≥ 60 mL/min/1.73 m² to < 15 mL/min/1.73 m². Prevalence of haemoglobin ≤ 10 g/dL increases substantially from 5.2% to 27.2% when glomerular filtration rate diminishes from ≥ 60 mL/min/1.73 m² to < 15 mL/min/1.73 m² (Hsu 2002; McClellan 2004; Stauffer 2014). The use of erythropoiesis stimulating agents (ESAs) has made significant improvements to managing anemia in CKD. However excessive use is associated with cardiovascular events and increased mortality (KDOQI 2006) such that the US Food and Drug Administration (FDA) has issued revised guidance on their use (FDA 2011). The importance of ESA use in combination with correction of ID is well-recognized, enabling anemia correction with lower doses of ESAs (Fishbane 1997; KDOQI 2006).

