11 STATISTICAL CONSIDERATIONS

11.1 SAMPLE SIZE AND POWER CALCULATIONS

A sample size of 135 subjects (Randomized 2:1, ferric maltol:Placebo, 90 in ferric maltol group and 45 placebo) will have 95% power to detect a statistically significant treatment difference of 1.0g/dL between ferric maltol and placebo on the primary endpoint, using a two-sided 0.05 significance level. This calculation assumes a common standard deviation of 1.5g/dl which is based on a pooled estimate of SDs obtained from published trials (Feraheme prescribing information 2010; Quinibi 2011; Macdougall 2014 Schwenk 2010; Singh 2006; Wyck 2005). Assuming a drop-out rate of 20%, approximately 168 subjects total will be recruited. Subjects randomization will be stratified based on baseline Hb value and eGFR.

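### Under 2:1 allocation the primary ANCOVA's standard error relies on equal spread in the two arms, which the documents neither show nor exclude; a robust or arm-specific standard error is a cheap safeguard.

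*Combined protocol and SAP*

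**What the plan says.** - Section 11.2.1 (Primary Endpoint Analysis) specifies ANCOVA with factors for treatment and disease and covariates for baseline Hb and eGFR, fitted to each of 10 imputed datasets. On inference it says: "By combining the results from these analyses, the treatment estimates will be constructed using the parameter estimates and associated standard errors". It mentions neither a robust standard error nor a separate variance per arm.
- Section 8.2 (Randomization) fixes the allocation: "Subjects will be randomized in a 2:1 ratio (ferric maltol:placebo").
- Section 11.1 (Sample Size) is the only place that speaks about spread: "This calculation assumes a common standard deviation of 1.5g/dl which is based on a pooled estimate of SDs obtained from published trials". It plans 90 evaluable subjects on ferric maltol and 45 on placebo.
- Section 11.2.3 lists four sensitivity analyses: per protocol, complete case, LOCF and MMRM. None is stated to relax equal variance between arms, and the MMRM covariance structure is not given. Other sensitivity analyses are left to the SAP, whose text is not among the pages supplied. Section 8.3 requires a final SAP before the randomization codes are released.

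**The concern.** The usual ANCOVA standard error estimates one residual variance from all subjects. With equal arms, a difference in spread largely cancels. At 2:1 it does not: the larger arm supplies about two thirds of the pooled variance, while the smaller arm contributes more than its share to the true sampling variance of the difference.

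This is the trial's single confirmatory test and interval, since Section 11.2.2 makes the other p-values descriptive. If ferric maltol subjects vary more than placebo subjects, the interval is too wide and some precision is lost. If placebo subjects vary more, the interval is too narrow, and the 5% level is exceeded when the means are equal but the spreads are not.

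**Working it through.** **Inputs from Section 11.1.** Difference 1.0 g/dL, common SD 1.5 g/dL, two-sided 0.05, 90 and 45 evaluable, 20% dropout, about 168 recruited (112 and 56 at 2:1). Arm-specific SDs are not given; every unequal pair below is an assumption.

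**The plan's own figure.** SE = 1.5 × √(1/90 + 1/45) = 0.274. Power = Φ(1.0/0.274 − 1.96) = Φ(1.69) = 95.5% (95.2% with the noncentral t). For dropout, 135/0.8 = 168.75. The stated 95% power and approximately 168 subjects reproduce.

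**Formulae**, with a = active SD, p = placebo SD:
- pooled variance s² = (89a² + 44p²)/133
- model SE = √[s²(1/90 + 1/45)]
- true SE = √(a²/90 + p²/45)
- R = model SE / true SE
- large-sample type I error = 2[1 − Φ(1.96R)]; coverage is its complement.

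**Active 1.6, placebo 1.2.** s² = (89 × 2.56 + 44 × 1.44)/133 = 2.19. Model SE = 0.270; true SE = √(0.0284 + 0.0320) = 0.246; R = 1.099. Type I error is 3.1% and coverage 96.9%. The 95% CI is 1.06 g/dL wide where 0.96 would be correct. Power at 1.0 g/dL is 97.2% with the pooled SE and 98.2% with the correct one.

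**Active 1.3, placebo 1.8.** s² = (89 × 1.69 + 44 × 3.24)/133 = 2.20. Model SE = 0.271; true SE = √(0.0188 + 0.0720) = 0.301; R = 0.899. Type I error is 7.8% and coverage 92.2%.

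**Smaller differences:**

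| Active / placebo SD | SD ratio | R | Type I error |
|---|---|---|---|
| 1.5 / 1.25 | 1.2 | 1.062 | 3.7% |
| 1.5 / 1.2 | 1.25 | 1.077 | 3.5% |
| 1.25 / 1.5 | 1.2 | 0.941 | 6.5% |
| 1.2 / 1.5 | 1.25 | 0.929 | 6.9% |

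**Cause.** At 112/56, R and the type I error change by no more than about 0.001, so a larger trial at 2:1 does not help. At 68/67 the pairs 1.6/1.2 and 1.3/1.8 give type I error of 4.9% and 5.1%. The allocation ratio is what exposes the test.

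**Does the remedy work with complete data?** Simulated ANCOVA with treatment and two covariates, 90/45, 20,000 runs (Monte Carlo SE about 0.15 points at 5%):

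| Active / placebo SD | Pooled | HC2 | HC3 | Arm-specific, Satterthwaite |
|---|---|---|---|---|
| 1.5 / 1.5, type I error | 5.1% | 5.1% | 4.7% | 5.0% |
| 1.5 / 1.0, type I error | 2.6% | 5.1% | 4.7% | 5.1% |
| 1.0 / 1.5, type I error | 8.4% | 5.1% | 4.7% | 4.9% |
| 1.5 / 1.5, power at 1.0 g/dL | 94.9% | 94.8% | 94.5% | 94.8% |

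**And with multiple imputation?** 112/56, 20% missing completely at random, 10 imputations, Rubin's rules, 4,000 runs (Monte Carlo SE about 0.34 points):

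| Active / placebo SD | Pooled SE, common imputation | HC2, common imputation | HC2, imputation by arm |
|---|---|---|---|
| 1.5 / 1.0, type I error | 2.8% | 4.6% | 5.3% |
| 1.0 / 1.5, type I error | 8.1% | 5.5% | 4.7% |

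The HC2 results are all within about 1.5 Monte Carlo SEs of 5%. The HC2 correction does most of the work. By-arm imputation is sound in principle, but its extra gain is too small to establish from these runs.

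**The case against.** The strongest reply is that nothing in the documents shows unequal spread. A reader might infer it from two places, and neither supports it.

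- Section 4.4 reports normal Hb at week 12 in 65% of treated and 10% of placebo subjects in the earlier IBD trial. That is a dichotomized outcome, and a uniform shift with identical SDs also yields partial response. Under normality with one threshold, the reported 2.25 g/dL difference fits a common SD of 2.25/(0.385 + 1.282) = 1.35 g/dL. This does not prove equality, because it mixes change with level and assumes a single cut-off, but the figures cannot be read as evidence of inequality.
- Section 4.1 says that "chronic inflammation can make absorption and utilization of iron less efficient compared to the normal state". That statement is not about variance, nor confined to the treated arm. The same section lists impaired dietary iron absorption as a cause of the anemia, and Section 6.4.2 permits iron-containing multivitamins in both arms.

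Three further replies carry weight. If treated subjects do vary more, the test is conservative and the loss is about one point of power. Inflated type I error needs equal means with unequal spread; if the drug did nothing to anyone, the arms would share one distribution and the pooled test would keep its level. And the pooled variance is itself inferred from the unqualified word ANCOVA and the common-SD assumption; Section 11.2.1 does not state it.

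All of this stands, and it limits how large a problem to expect. It does not answer the main point: the validity of the confirmatory interval rests on an assumption that no supplied text supports beyond planning, and that 2:1 allocation makes consequential.

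**Conclusion.** The point holds as a low-cost robustness improvement. Plain ANCOVA is a conventional primary analysis, and the sample size is unaffected. If the arms differ in spread, the pooled standard error is off by about 10% in either direction at SDs of 1.6/1.2 or 1.3/1.8, and by about 6 to 8% at ratios of 1.2 to 1.25. These pairs are assumptions; the documents supply neither the size nor the direction of any difference.

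It would go too far to say that the planned interval or p-value is wrong, or that the false-positive rate will exceed 5%. The documents do not show that the arms will differ, and one of the two directions is only conservative. It would also go too far to ask for arm-specific covariance in the MMRM: with about 56 placebo subjects, its cost has not been shown.

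**What to change.** Before unblinding, state in the SAP that:

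1. within each imputed dataset the ANCOVA treatment estimate is kept, but its standard error is HC2 (or HC3), or allows a separate residual variance per arm with Satterthwaite degrees of freedom, before Rubin's rules are applied;
2. imputation is run separately by arm, so that imputed values do not reimpose a common variance;
3. the pooled-variance result is reported as a check.

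HC2 and the arm-specific form held the 5% level slightly more closely than HC3, which was a little conservative.

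The cost is a few SAP sentences and a programming option. N and the form of the treatment estimate do not change. If the SDs are equal, the interval is 0 to 1.5% wider (1.5% for HC3) and power falls by at most about half a point. If placebo subjects vary more, the corrected interval is wider (1.18 against 1.06 g/dL at 1.3/1.8), which is the width needed for 95% coverage. Fixing the choice now also avoids a change of standard error after unblinding that would look data-driven.
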